### 164 **3.4.3.2** Control group

- Patients in the control group receive insulin dosage titration set by senior physicians based onSMBG and clinical information.
- 167 **3.5 Study Outcomes**
- 168 **3.5.1 Primary outcomes**
- 169 The percentage of time of sensor glucose measurements in targeted range (3.9-10 mmol/L) during
- 170 the 5-days trial period.
- 171 **3.5.2 Secondary outcomes**
- 1. The percentage of time of sensor glucose measurement above range (10.1-13.9 mmol/L) during
  the 5 days trial period;
- 174
  2. The percentage of time of sensor glucose measurement above range (>13.9 mmol/L) during the
  175
  5 days trial period;
- 176 3. The percentage of time of sensor glucose measurement below range (3.0-3.8 mmol/L) during
  177 the 5 days trial period;
- 4. The percentage of time of sensor glucose measurement below range (<3.0 mmol/L) during the

  5 days trial period;
- 180 5. The mean sensor glucose concentration;

- 181 6. The glucose management indicator (GMI);
- 182 7. The glycemic variability (%CV);
- 183 8. The mean pre-meal and pre-bed capillary glucose concentration at each defined time based on
- 184 SMBG;
- 185 9. The risk of incidence of hypoglycemia events;
- 186 10. The risk of incidence of hyperglycemic events;
- 187 11. The mean total daily insulin dose.

#### 188 4 Safety and Adverse Events

#### 189 **4.1 Definition of Adverse Events**

190 The included hospitalized T2D patients with insulin therapy might develop hypoglycemia, 191 hyperglycemia events with/without diabetic ketoacidosis or with/without hyperosmotic state, or 192 other adverse events during the trial period.

### 193 **4.1.1 Hypoglycemia**

- 194 We determine the number of patients with hypoglycemia as defined by the Joint Position Statement
- 195 of the American Diabetes Association and the European Association for the Study of Diabetes.
- 196 Minor hypoglycemia is defined as a recorded capillary blood glucose level <3.9 mmol/L, which the
- 197 patient has been able to self-treat. Clinical significant hypoglycemia is defined as a recorded
- 198 capillary blood glucose level <3.0 mmol/L. Severe hypoglycemia events are defined as a capillary
- $199 \qquad \text{glucose level} < 2.2 \text{ mmol/L or an episode that requires of assistance of another person due to severe}$
- 200 impairment in consciousness or behavior.

### 201 4.1.2 Acute hyperglycemia complications of type 2 diabetes

202 Capillary blood glucose >20.0 mmol/L, and/or ketoacidosis, and/or hyperosmotic status.

### 203 4.1.3 Other Adverse Events

- An adverse event can be any unfavorable and unintended sign (e.g. an abnormal laboratory finding), symptom (for example nausea, chest pain), or disease temporally associated with the use of a medical product, whether considered related to the medical product.
- 200 medical product, whether considered related to the m

# 207 **4.1.4 Severe adverse events**

- According to the definition by the Food and Drug Administration, USA, severe adverse events are defined as any of the following:
  - Life-threatening experience
  - Death

210

211

214

- Prolongation of existing hospitalization
- A persistent or significant disability/incapacity
  - A congenital anomaly/birth defect

### 215 **4.2 Recording and Reporting of Adverse Events**

- All non-serious and serious adverse events will be collected from the time of signature of informed consent until the end of the trial and recorded in the case report form. The occurrence time, clinical manifestation, treatment, duration, and outcome should be recorded in detail in the case report form. If an abnormal laboratory examination occurs, the patient should be followed up until the results of the examination return to normal, or to the level before treatment, or to determine if it is not related to the treatment.
- If severe adverse events occur in participants, physicians should immediately provide the appropriate care to ensure their safety. Additionally, physicians will report the adverse events and

treatment to the Principal Investigator and the Committee within 24 hours and complete the report

225 form.

# 226 **4.3 Safety Monitoring**

227 In the course of the study, an expert committee will be set up, which consists of two chief physicians 228 who are independent of the two groups. The expert committee will review the trial program and 229 adverse events and make a decision of continuing or suspension of the study. If the patient develops 230 severe hyperglycemia events (capillary blood glucose >20.0mmol/L), or clinical significant and 231 severe hypoglycemia (capillary blood glucose <3.0mmol/L), the expert committee will review the 232 regimen provided by the iNCDSS. If the recommendation of iNCDSS system is consistent with that 233 of the expert committee, patients continue to be treated in accordance with the insulin dosage 234 titration recommended by the iNCDSS; else if the expert committee does not endorse the insulin 235 dosage titration recommended by the iNCDSS, then the patient will be judged to withdraw from the 236 study and receive treatment by physicians. If patients suffer from severe events such as ketoacidosis, 237 and/or hypertonic coma, the patients will be judged to terminate the study and receive an 238 intravenous infusion of insulin treatment. And if patients suffer from hypoglycemia coma, the 239 patients will be judged to terminate the study and receive an intravenous infusion of glucose 240 therapy.

All case report forms for each participant should be filled out by study staff in a timely manner. The case report form should be double-checked for potential errors or missing data prior to patients leaving the clinic. Original documents and case report forms will be stored in the study office. All data will be double-entered by researcher staff. Whenever inconsistencies are found, the data will be corrected by re-examination of the original case report forms or laboratory reports.

246 5 Participant Termination

247 Patients may be terminated in the following situations:

- 248 1) Patients request to withdraw from the study;
- 249 2) The expert committee suggests terminating the study for a medical perspective;
- 250 3) Adverse events or other unexpected reasons.

At any time, patients are free to discontinue or withdraw from the study, without prejudice for further treatment. A patient who decides to withdraw from the study will always be asked about the reason(s) and the presence of any adverse events. If possible, they will be seen and assessed by an investigator(s). Adverse events will be followed up.

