## 79 3. Study Design

### 80 3.1 Design Overview

81 The study is a multicenter, patient-blind, and randomized controlled trial to evaluate the efficacy 82 and safety of iNCDSS in the clinical application. Eligible patients are randomly allocated into two 83 groups at a ratio of 1:1 after screening and run-in period. Randomization is stratified according to 84 sites and baseline HbA1c level. Patients in the intervention group receive insulin dosage titration set 85 by the iNCDSS assisted system and patients in the control group receive insulin dosage titration set 86 by senior physicians. A total of 142 type 2 diabetic patients will be enrolled and this study will be 87 conducted in the wards of Department of Endocrinology and Metabolism in Zhongshan Hospital, 88 Xuhui Central Hospital, and Shanghai Fifth People's Hospital, Fudan University. All patients are 89 studied for 5 consecutive days. Continuous glucose monitoring (CGM) is performed using flash 90 glucose monitoring (Abbott Freestyle Libre, USA) to measure the primary outcome of the 91 percentage of time of sensor glucose concentration in the target range during the 5 days trial period. 92 The CGM data will be analyzed retrospectively, and the treatment will not be influenced by data 93 gained by CGM. 94 **3.2 Study Population** 

- Eligible patients should meet the inclusion criteria and be excluded from the study if they meet anyof the exclusion criteria.
- 97 **3.2.1 Inclusion criteria**
- 98 Patients included in this study should meet the following criteria:
- 99 1) Patients with type 2 diabetes;
- 100 2) Aged  $\geq 18$  years old;
- 101 3) Treated with diet alone, any combination of oral antidiabetic agents, and/or insulin

therapy for at least 3 months;

103 4) HbA1c: 7.0%-11.0%.

104 **3.2.2 Exclusion criteria** 

- 105 Patients will be excluded from this study if they meet any of the following exclusion criteria:
- Acute diabetic complications including diabetic ketoacidosis or hyperglycemic
   hyperosmolar state;
- 108 2) BMI≥45 kg/m^2;
- 109 3) Women who are pregnant or breast-feeding;
- 110 4) Subjects with severe cardiac, hepatic, or renal diseases;
- 111 5) Subjects with any psychiatric or psychological diseases;
- 112 6) Subjects with severe oedema, infections, or peripheral circulation disorders;
- 113 7) Patients plan to receive surgery during hospitalization;
- 114 8) Subjects who cannot comply with the protocol.

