# 152 **3.4.3 Intervention period**

## 153 **3.4.3.1 Intervention group**

154 The iNCDSS system is an artificial intelligence-based insulin clinical decision support system using 155 an artificial intelligence-based system to extract clinically relevant features from EHR notes to 156 mimic the insulin dosage titration by senior endocrinology physicians. The iNCDSS is installed in 157 the doctor's advice interface of the health information system (HIS) to real-time read patient 158 information and provide insulin dosage regimens. In the intervention group, insulin dosage is modified and titrated according to the iNCDSS recommendation. The physicians can review the 159 160 current recommendation and choose "accept" or "reject". The nurse staff will conduct insulin 161 injection according to the doctor prescribed. To assess compliance, physicians' adherence to the 162 recommended insulin dosage will be documented and any deviation from recommended dosage to 163 administered insulin dosage will be recorded.

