## 255 6 Statistical Analyses

## 256 6.1 Sample Size Estimate

257 The design of this study is a non-inferiority randomized clinical trial to explore the efficacy and 258 safety of the iNCDSS compared with senior physicians. The sample size calculation was based on 259 the primary outcome. According to our previous study, the proportion of time the sensor glucose 260 measurement in the target glucose range of 3.9-10.0 mmol/L during the intervention period was 261 80% with a standard deviation of 0.12. A margin of 6 percentage points was calculated to assess 262 non-inferiority in the difference in the TIR between the groups. We calculated that 142 patients 263 were needed (considering a dropout rate of approximately 10%) to achieve a power of 80% with an 264  $\alpha$  value of 0.025 (one-sided 95% CI).

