### 265 6.2 Data Analysis and Interpretation

Values are presented as mean (SD), median (IQR) or number (%), unless stated otherwise. All analyses are performed by intention-to-treat, and all patients who have available CGM data are 268 included in the primary analysis and all secondary analyses unless otherwise noted. All efficacy 269 outcomes and continuous glucose monitoring based outcomes are summarized and analyzed using 270 the intervention period and intention-to-treat analysis set, and safety analyses included all data up to 271 the end of the study. The primary and secondary outcomes are compared between the two groups 272 with a linear mixed-effect regression model. Missing data are not imputed. The noninferiority 273 hypothesis is tested for the primary outcome by estimating the difference in the percentage of sensor 274 glucose measurement in TIR between the iNCDSS group and the physician group, and the lower limit of 95% CI of -6.0% is estimated as the noninferiority threshold. The proportion of participants 275 276 with events (capillary glucose concentrations <3.0 mmol/L, <2.2 mmol/L, >20.0mmol/L, and/or 277 ketoacidosis) in each group is compared with Fisher's exact test. Compliance is calculated as the 278 percentage of the number of insulin orders where dosages are actually ordered according to 279 iNCDSS recommendation against the total number of insulin orders. All statistical analyses are 280 performed with the use of SAS 9.3 software and R software.

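### Committee rejection of an iNCDSS dose removes the patient from the study, in the iNCDSS arm only, so time-in-range days can be lost for outcome-related reasons

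*Protocol*

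**What the plan says.** Protocol section 4.3 sets the trigger at a capillary glucose above 20.0 mmol/L or below 3.0 mmol/L. The expert committee then reviews the iNCDSS regimen. If it agrees with the recommendation, the patient stays on iNCDSS titration. If it does not endorse the "dosage titration recommended by the iNCDSS, then the patient will be judged to withdraw from the" "study and receive treatment by physicians". Both branches depend on an iNCDSS recommendation. Control patients are dosed by senior physicians (section 3.4.3.2), and no corresponding review or withdrawal is written for them. The terminations for ketoacidosis or coma in section 4.3, and the general grounds in section 5, name no arm.

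The primary outcome (section 3.5.1) is the percentage of time with sensor glucose at 3.9–10 mmol/L over the five-day period. On the analysis, section 6.2 says "analyses are performed by intention-to-treat, and all patients who have available CGM data are" included, and adds "Missing data are not imputed".

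Two other passages bear on the point. Under section 3.4.3.1 a ward physician may reject an iNCDSS dose. Adherence to the "recommended insulin dosage will be documented and any deviation from recommended dosage to" the dose given is recorded, and no withdrawal follows. Section 3.1 says of the sensor: "The CGM data will be analyzed retrospectively, and the treatment will not be influenced by data" from it.

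**The concern.** The rule takes the patient out of the study, not merely off the algorithm. Its trigger is closely tied to the endpoint, because both thresholds lie outside the target range that defines TIR. Patients are thus selected for removal after randomisation, on poor glucose control, by a mechanism that exists in one arm. Nothing in the protocol says that CGM continues afterwards, and section 6.2 uses only the data available.

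Not everything is lost. CGM before withdrawal remains, and so does the Fisher comparison of threshold events. What can be lost is TIR after withdrawal.

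The effect could go either way. If the missing days would have been poor, losing them flatters iNCDSS and raises the chance of a false non-inferiority claim. If they would have been recovery days under physician dosing, losing them counts against iNCDSS and costs power.

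**Working it through.** **The plan's own figure.** Section 6.1 assumes TIR of "80% with a standard deviation of 0.12" (12 percentage points), a margin of 6 points, one-sided α of 0.025, 80% power and about 10% dropout. Allocation is 1:1. With the noncentral t distribution, 64 patients per arm give 80.1% power, so the total is 128, and 128/0.9 = 142.2. The stated 142 reproduces, and no stated figure is in dispute.

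**Precision.** With 64 analysed per arm:

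SE = 12 × √(2/64) = 2.12 points; df = 126; t = 1.979.

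**Bias from lost days.** Take one TIR value per patient and let 3 of the 5 days be lost. With mean TIR R on retained days and L on lost days:

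- full five-day TIR = (2R + 3L)/5
- recorded TIR = R
- error for that patient = R − (2R + 3L)/5 = 0.6 × (R − L)
- bias in the difference, iNCDSS minus physician: b = share withdrawn × 0.6 × (R − L)

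Example: 0.05 × 0.6 × 15 = +0.45 points.

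**Consequences.**

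- False non-inferiority is the probability that the lower 95% limit exceeds −6 when the true difference is −6. It is the upper tail beyond 1.979 of a noncentral t with noncentrality b/2.12.
- Power at no true difference uses noncentrality (6 + b)/2.12.

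The documents give neither the share withdrawn nor the TIR gap. Those two inputs, and the 3 days lost, are assumptions. Of 142/2 = 71 randomised per arm, 5% is about 4 patients and 3% about 2.

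| Share withdrawn | Lost days vs the same patient's retained days | Bias (points) | False non-inferiority | Power at no true difference |
|---|---|---|---|---|
| 5% | 30 points worse | +0.90 | 6.2% | not a loss |
| 5% | 15 points worse | +0.45 | 4.0% | not a loss |
| 3% | 15 points worse | +0.27 | 3.3% | not a loss |
| any | equal | 0 | 2.5% | 80.1% |
| 3% | 15 points better | −0.27 | 1.8% | 76.4% |
| 5% | 15 points better | −0.45 | 1.5% | 73.8% |
| 5% | 30 points better | −0.90 | 0.9% | 66.5% |

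**Sections 4.3 and 3.4.3.1 side by side.** When a ward physician overrides the algorithm, the patient stays and the deviation is logged. When the committee overrides it, participation ends. The first rule shows that overriding a dose while keeping the patient in the trial is already workable here.

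**The case against.** The best counter-arguments are these.

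- **Other exits exist in both arms.** Section 5 allows any patient to be terminated for adverse events or on the committee's medical advice, so outcome-related loss is possible among controls too. That is true, but those grounds are discretionary. They are not a glucose-triggered rule matching the one in section 4.3, and the one-arm point concerns only that rule.
- **A safety check on new software is reasonable.** The control arm has no algorithm dose to endorse. This stands as a reason for the review. It does not explain why disagreement should end study participation rather than iNCDSS dosing. Likewise, a refusal after an extreme glucose is more serious than a routine rejection of one order, so the contrast with section 3.4.3.1 is a tension, not a contradiction.
- **Loss of CGM is inferred.** No text says that the sensor comes off, and the SAP may say how partial records are handled. But withdrawal from the study ordinarily ends data collection, and no SAP can recover days that were not collected.
- **The size may be small and the direction benign.** Ward physicians can already reject doses, withdrawals over five days may be few, and recovery under physician dosing is at least as plausible as further poor days. With 1 of 71 withdrawn and lost days 15 points worse, the bias is 15 × 0.6/71 = 0.13 points and the error 2.9%. This stands, and it limits the claim about size.
- **The formula fits one form of the analysis.** Section 6.2 names a linear mixed-effect model without stating the unit of response. If that unit is daily TIR, the model could partly account for dropout that depends on observed glucose. This also stands, and the table is an illustration only.

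**Conclusion.** The concern holds and should be fixed. As written, section 4.3 can shorten the outcome window for reasons tied to the outcome, through a rule with no control-arm counterpart, and section 6.2 calls the resulting comparison intention-to-treat. Confidence in that reading is high.

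Confidence in direction and size is low to moderate. Over the tabulated range (3–5% withdrawn, 3 of 5 days lost, a gap of 15 to 30 points either way), false non-inferiority runs from 0.9% to 6.2% against a nominal 2.5%, and power can fall from 80.1% to 66.5%. With a single withdrawal the effect is slight. With a 6-point margin and about 64 analysed per arm, a handful of withdrawals can matter.

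**What to change.** Amend sections 4.3, 5 and 6.2 as follows:

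- When the committee does not endorse the recommendation, iNCDSS titration stops and physicians take over dosing, but the patient remains in the study.
- CGM continues to day 5 for every randomised patient unless consent to data collection is withdrawn.
- All these days enter the primary analysis under the assigned arm.
- The override is logged as a deviation, as section 3.4.3.1 already does for a ward physician's rejection.

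The cost is small: the sensor is already worn and does not guide treatment, so patient protection is unchanged. The drawback is that some iNCDSS-arm days will reflect physician dosing. That pulls the arms together, which in a non-inferiority trial favours the claim. A sensitivity analysis that scores post-override days unfavourably would guard against this and can be left to the SAP.

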## 255 6 Statistical Analyses

## 256 6.1 Sample Size Estimate

257 The design of this study is a non-inferiority randomized clinical trial to explore the efficacy and 258 safety of the iNCDSS compared with senior physicians. The sample size calculation was based on 259 the primary outcome. According to our previous study, the proportion of time the sensor glucose 260 measurement in the target glucose range of 3.9-10.0 mmol/L during the intervention period was 261 80% with a standard deviation of 0.12. A margin of 6 percentage points was calculated to assess 262 non-inferiority in the difference in the TIR between the groups. We calculated that 142 patients 263 were needed (considering a dropout rate of approximately 10%) to achieve a power of 80% with an 264  $\alpha$  value of 0.025 (one-sided 95% CI).

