## 115 **3.3 Randomization and masking**

## 116 **3.3.1 Randomization**

Randomization will be conducted by the statistician of Department of Statistics, Public Health and Preventive Medicine, Fudan University, and generated by SAS software. The randomization scheme is generated and concealed until an eligible participant is ready to be randomized. Prior to randomization, the study coordinator should confirm that all screening procedures have been completed, the participant meets all eligibility criteria, and all required baseline data have been collected. Randomization is stratified according to sites and HbA1c levels (<8.0% or  $\geq$ 8.0%) and

eligible patients are randomly allocated into intervention and control groups at a ratio of 1:1.

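### Section 6.1 labels a one-sided α of 0.025 as a one-sided 95% CI, which is an α = 0.05 rule, and section 6.2 does not state the sidedness of the deciding interval

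*Protocol*

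**What the plan says.** Protocol section 6.1 (Sample Size Estimate) sizes the trial on time in range (TIR). The assumptions are "80% with a standard deviation of 0.12", a 6-point non-inferiority margin, 80% power and roughly 10% dropout, and the result is 142 patients. The test level is an α "value of 0.025 (one-sided 95% CI"), the interval being given in brackets as a gloss on the α.

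Section 6.2 (Data Analysis and Interpretation) holds the decision rule. The difference in TIR between the iNCDSS group and the physician group is estimated, and the lower "limit of 95% CI of -6.0% is estimated as the noninferiority threshold". This sentence does not say whether the interval is one-sided or two-sided. The bracket in 6.1 is the only place in the protocol that gives the interval a sidedness.

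**The concern.** An α and a confidence level are two descriptions of one rule and have to agree. A one-sided 95% lower bound lies 1.645 standard errors below the estimate and tests at 0.05. The lower limit of a two-sided 95% CI lies 1.960 standard errors below it and tests at one-sided 0.025. The pair in 6.1 joins the α of the second rule to the interval of the first.

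The mismatch reaches beyond the sample-size paragraph because 6.2 needs exactly the word that 6.1 gets wrong. An analyst who asks which 95% CI is meant finds one answer in the protocol, and it contradicts the α printed beside it. The rule decides the trial's only primary hypothesis, and the looser reading favours a finding of non-inferiority. The choice should therefore not be open when the data are seen.

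**Working it through.** **Inputs (Protocol section 6.1 unless noted)**
- Margin 6 points: "A margin of 6 percentage points was calculated to assess" non-inferiority.
- SD 0.12, i.e. 12 points of TIR.
- Power: "to achieve a power of 80% with an" α of 0.025.
- Dropout: "considering a dropout rate of approximately 10"%.
- Allocation (section 3.3.1): "randomly allocated into intervention and control groups at a ratio of 1:1".
- Stated total: "We calculated that 142 patients".
- True difference: not stated; taken as 0.

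**Step 1. Reproduce the plan's figure with one-sided 0.025**

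n per arm = 2 × (z for α + z for power)² × (SD/margin)²

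= 2 × (1.960 + 0.842)² × (12/6)² = 62.8, so 63 per arm.

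With 10% dropout, 63/0.9 = 70 per arm, 140 in all. The t-test version needs 64 per arm (power 80.1%), and 128/0.9 = 142.2, which is the stated 142.

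**Step 2. Repeat with the α that a one-sided 95% CI implies**

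2 × (1.645 + 0.842)² × (12/6)² = 49.5, so 50 per arm.

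With dropout, 50/0.9 = 55.6, so 56 per arm and 112 in all. The t-test version needs 51 per arm; 102/0.9 = 113.3, or 114 if each arm is rounded up. Neither is near 142.

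The trial was therefore sized for one-sided 0.025, and the interval label is the half that is wrong.

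**Step 3. What the label would do if applied literally**

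Take 64 evaluable patients per arm and an unadjusted comparison. SE = 12 × √(2/64) = 2.12 points. The lowest observed difference that passes is -6 plus the critical value times SE, with 126 degrees of freedom for the t values.

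| | Lower limit of two-sided 95% CI | One-sided 95% CI |
|---|---|---|
| Type I error at a true difference of -6 | 2.5% | 5.0% |
| Lowest passing estimate, t | -6 + 1.979 × 2.121 = -1.80 | -6 + 1.657 × 2.121 = -2.48 |
| Lowest passing estimate, z | -1.84 | -2.51 |
| Power at a true difference of 0, t | 80.1% | 87.9% |
| Power at a true difference of 0, z | 80.7% | 88.2% |

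An observed difference between about -2.5 and -1.8 points would be non-inferior under one reading and not under the other.

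**The case against.** The strongest reply is that the intended rule can be recovered. The stated α is 0.025, the sample size reproduces only at 0.025, and the 95% CI in 6.2, read in the ordinary way as two-sided, is also a one-sided 0.025 test. Three elements agree and one bracket does not, so a mislabel is the likely explanation. This stands, and it is why the point concerns the label and not the design.

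Two stronger readings are tempting, and the protocol supports neither:
- A reader might infer that the decision rule contradicts itself. It does not. The contradiction lies within 6.1; the sentence in 6.2 is incomplete but consistent with α = 0.025. Nor does reading 6.2 together with 6.1 make the one-sided 95% interval the prescribed one, because 6.1 also states the α.
- A reader might infer that the plan doubles the false non-inferiority rate. That happens only if the bracket is followed and the stated α beside it is set aside.

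It can also be said that the sidedness of an interval is commonly left to a statistical analysis plan, which is not at hand here. That is fair as to the silence of 6.2 taken alone. It does not excuse 6.1, which states the sidedness and states it wrongly.

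Finally, the two readings differ over a window of only about 0.7 points, and the threshold of -6.0 points is the same in both sections. Both are true, and they limit the size of the point. They do not settle which confidence level decides the primary claim.

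**Conclusion.** The point holds as a mislabelled confidence level. Section 6.1 equates one-sided α = 0.025 with a one-sided 95% CI, which is false, and 6.2 does not correct it. The sample size identifies 0.025 as the level used, given the assumed true difference of 0.

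The consequence is conditional. If the label were applied literally, the type I error at the margin would be 5% instead of 2.5%, and the lowest passing estimate would move from about -1.8 to about -2.5 points. These cut-offs assume 64 evaluable per arm, an SD of 12 points and an unadjusted comparison. Section 6.2 plans a linear mixed-effect model, whose standard error may differ and shift both. The margin, the power statement and the total of 142 are not in question. Because the wording governs the primary non-inferiority decision, it is more than clerical and should be settled before the data are analysed.

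**What to change.** In section 6.1, replace the bracketed label so that the level reads: *one-sided α = 0.025 (lower limit of the two-sided 95% CI, i.e. one-sided 97.5% CI)*.

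In section 6.2, state the rule in full: *non-inferiority is concluded if the lower limit of the two-sided 95% CI for iNCDSS minus physician TIR is above -6.0 percentage points*.

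The cost is two sentences of protocol wording. The sample size, the margin and the planned model do not change.
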